6.2.2. Statistical Hypothesis for Clinical Efficacy Endpoint

The null statistical hypotheses to be tested can be stated as the survival and hazard functions being identical between SEL 18 mg (SEL 6 mg) and placebo.

6.2.3. Analysis of Clinical Efficacy Endpoint

Differences in EFS between SEL 18 mg (SEL 6 mg) and placebo will be assessed using the log-rank test stratified by presence or absence of diabetes mellitus and ELF test score ≥ 9.76 or < 9.76 at baseline.

Time (in months) to the first clinical event/censoring date will be calculated as: $[\text{first clinical event date or censoring date} - \text{randomization date} + 1] / 30.4375$.

Censoring date will be the later date between the last visit date and latest AE onset date in the Randomized Phase for subjects who have prematurely discontinued from the Randomized Phase, or who have completed the Randomized Phase. For the Week 48 Interim Analysis, the data cut date will be used as the censoring date for ongoing subjects in the Randomized Phase.

For the purpose of analysis, if the onset date of a clinical event or an AE is incomplete, the first day of the month (if date is missing) or the first day of the year (if date and month are missing) will be used to derive the clinical event or censoring date. If such imputation leads to an imputed event date that is earlier than the randomization date, then the randomization date should be used to impute the incomplete event date.

In the following code, *Months* is the number of months from randomization date to the first clinical event or to the censoring date for subjects who don't have clinical events. *Status* is a binary variable with 1 representing no clinical event observed and 0 representing a clinical event observed.

```
proc lifetest data=efs_2groups;  
    time Months*Status(1);  
    strata BL_Diabetes BL_ELF_category / group=treatment;  
run;
```

A proportional hazards model will be used to calculate the point estimate and 95% CIs for the hazard ratio between SEL 18 mg (SEL 6 mg) and placebo controlling for stratification factors. Proportional hazard assumption will be evaluated.

```
proc phreg data=efs_3groups;  
    class treatment BL_Diabetes BL_ELF_category;  
    model Months*Status(1) = treatment / RL;  
    strata BL_Diabetes BL_ELF_category;  
run;
```

For each treatment group, the KM estimates of EFS probability at 3-month intervals (ie, at Month 3, 6, 9, etc) and 95% CIs will be provided. The 95% CI will be calculated based on Greenwood's formula and log-log transformation of the survival function.

Median, Q1 and Q3 of the EFS will be provided for each treatment group. The 95% CI for median EFS based on Brookmeyer-Crowley method {[Brookmeyer 1982](#)} of inverting a generalization of the sign test for censored data will also be provided for each treatment group.

Kaplan-Meier curves will be plotted for the clinical EFS by treatment arm. A by-subject listing of clinical events will be provided.

A sensitivity analysis of EFS will be performed where mortality includes only liver-related death. All deaths will be reviewed by the Hepatic Event Adjudication Committee to determine if they are liver-related.

In addition, a sensitivity analysis for the clinical efficacy endpoint will be performed by using the KMMI approach as described in Section 3.6.1 if the survival functions of SEL 18 mg (SEL 6 mg) and placebo are demonstrated to be significantly different (in favor of SEL 18 mg or SEL 6 mg).

Forest plots of treatment effect in the clinical efficacy endpoints, assessed by the hazard ratios between each SEL arm and placebo arm, will be generated for the Week 48 interim analysis and the Week 240 final analysis. Forest plots for subgroup analyses will be generated in the final analysis at Week 240.

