To confirm the anti-fibrotic activity of SEL, this Phase 3 study has been designed as a multicenter, randomized, double-blind, placebo-controlled trial evaluating the safety and efficacy of SEL for 240 weeks in subjects with NASH and advanced fibrosis. Eight hundred subjects with histologically-confirmed NASH and bridging (F3) fibrosis (according to the NASH CRN classification) will be randomized in a 2:2:1 ratio to receive SEL at a dose of 6 mg or 18 mg orally once daily or placebo. Randomization will be stratified by the presence of diabetes mellitus, a common comorbidity in this condition, and ELFTM score ( $< 9.76$  vs.  $\geq 9.76$ ) during Screening. In the Phase 2b study GS-US-321-0105 of SIM, an ELFTM score  $\geq 9.76$  was associated with an increased risk of liver-related clinical events (area under the receiver operating characteristic [AUROC] curve, 0.794). The primary objective of this study is to evaluate whether SEL can cause fibrosis regression and prevent progression to cirrhosis in this high-risk patient population. Efficacy will be determined by changes in liver histology and adjudicated hepatic clinical event rates that include hepatic decompensation, liver transplantation, and all-cause mortality. Due to the increased risk of cardiovascular morbidity and mortality in NASH {Angulo 2015, Ekstedt 2015, Targher 2016}, the impact of SEL on metabolic parameters (e.g., lipids and insulin resistance) will be monitored and cardiovascular events will be prospectively recorded and adjudicated.

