1.3. Sample Size and Power

With a sample size of 320 subjects in each active treatment arm and 160 subjects in the placebo arm, the study has 94% power to detect a difference in the proportion of subjects with a ≥ 1 -stage improvement in fibrosis without worsening of NASH of 15% or more at Week 48 at a significance level of 0.025 (2-sided), assuming the proportion of subjects that meet the endpoint in the placebo arm is 12%.

With regard to the clinical efficacy endpoint, subjects will be followed for a period of up to 240 weeks. The estimate of the expected event rate is 30% in untreated patients, producing an expected EFS rate of 70% at 240 weeks in the placebo arm. SEL is expected to improve the EFS rate to 83.7% (expected event rate of 16.3%) compared with placebo (hazard ratio (HR), 0.50). We also expect a 20% overall dropout rate. Given the above assumptions, for comparison of the SEL arms versus the placebo arm, together with a total sample size of 800 subjects (2:2:1 ratio), and assuming the log-rank test statistic is evaluated using a 2-sided 0.025 significance level, the study will have 85% power to evaluate the superiority of each SEL arm versus placebo with respect to EFS.

Therefore, the overall power for the trial, assuming independence between the primary efficacy endpoint and clinical efficacy endpoint, is 80% ($94\% \times 85\%$). It should be noted that this is a lower bound estimate as these 2 endpoints are expected to be positively correlated.

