3.3. Strata and Covariates

An Interactive Web Response System (IWRS) will be used for centralized randomization and treatment assignment. Randomization will be stratified by

- Presence or absence of diabetes mellitus (as determined by medical history or based on Screening laboratory values if previously undiagnosed [i.e. HbA1c \geq 6.5% or fasting plasma glucose \geq 126 mg/dL])
- ELF score \geq 9.76 or $<$ 9.76 during Screening.

If there are discrepancies in stratification factor values between the IWRS and the clinical database, the baseline values recorded in the clinical database will be used for analyses.

Efficacy endpoints will be evaluated using stratification factors as covariates for analyses, as specified in Section 6.

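### The EFS test and hazard ratio use ELF only as above or below 9.76, which gives up some efficiency; the size of the loss depends on a prognostic strength the documents do not state

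*SAP*

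**What the plan says.** SAP 6.2.3 compares each selonsertib arm with placebo on EFS by a "log-rank test stratified by presence or absence of diabetes mellitus and ELF test score", with ELF in two levels split at 9.76. The hazard ratio comes from a Cox model with the same two-level strata and one term: "model Months*Status(1) = treatment / RL". SAP 3.3 sets the general rule: "Efficacy endpoints will be evaluated using stratification factors as covariates for analyses". Neither EFS sensitivity analysis in 6.2.3 (liver-related deaths only; Kaplan-Meier multiple imputation) uses the ELF value itself. Protocol 8.6.1 and the synopsis also name the stratified log-rank test.

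The numerical score is collected. Under protocol 5.1 the IWRS stratifies on Screening ELF, SAP 5.2 lists the ELF test score as a baseline characteristic, and SAP Appendix 7 has a rule for components outside the limits of quantitation. That every randomised subject has a usable score is an inference from these passages; the documents do not say so directly.

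Protocol 1.3 explains why ELF was chosen. In an earlier simtuzumab Phase 2b study, a score of at least 9.76 "was associated with an increased risk of liver-related clinical events (area under the receiver operating characteristic [AUROC] curve, 0.794".

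**The concern.** Stratified randomisation needs categories; the analysis does not. Two levels treat scores just either side of 9.76 as different and all scores above it as alike. Whatever ELF predicts within a level stays as unexplained variation in risk. In a time-to-event comparison that variation pulls the treatment contrast towards the null and lowers power.

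EFS is where this would count. Its stated power is 85% per arm, against 94% for the Week 48 histology endpoint, and enrolment is planned at about 800. Adjusting for a baseline value already held is one of the few ways to gain information without more subjects or longer follow-up.

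**Working it through.** **Inputs from SAP 1.3.** "With a sample size of 320 subjects in each active treatment arm and 160 subjects in the placebo arm"; "The estimate of the expected event rate is 30% in untreated patients"; "SEL is expected to improve the EFS rate to 83.7% (expected event rate of 16.3%) compared with placebo (hazard ratio (HR), 0.50"; 20% overall dropout; 240 weeks; "assuming the log-rank test statistic is evaluated using a 2-sided 0.025 significance level". The hazard ratio is consistent with the rates: ln 0.837 / ln 0.70 = 0.499.

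**Assumptions, not in the documents.** ELF is normal and log-linear on the hazard; its AUROC for EFS lies between 0.60 and 0.794; half of subjects are above 9.76 (varied from 40 to 60%); 70% have diabetes, with no effect on EFS; dropout is exponential.

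**Step 1: reproduce the 85%.**

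- Without dropout, events = 160 × 0.30 + 320 × 0.163 = 48 + 52.2 = 100.2. Schoenfeld: √(100.2 × 2/3 × 1/3) × ln 2 − 2.241 = 1.03, so power is 84.8%.
- With 20% exponential dropout, events = 43.3 + 47.0 = 90.3. Using variance 1/43.3 + 1/47.0 for the log hazard ratio, ln 2 / 0.2107 − 2.241 = 1.05, so power is 85.3%. A simulated log-rank test gives 84.6%. Schoenfeld on 90.3 events gives 80.6%.

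The stated figure reproduces.

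**Step 2: what the split discards.** For a normal score cut at its median, the two-level factor keeps 2/π = 64% of the variance, so about 36% is left within levels.

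**Step 3: value of the continuous score.** Simulated trials of 320 against 160, with event rates held at 30% and 16.3% and ELF's effect set to give each AUROC. The planned four-stratum log-rank was compared with the Cox score test that adds continuous ELF within the same four strata. Because Z grows with the square root of events, the equivalent gain is (mean Z adjusted / mean Z planned)² − 1.

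| AUROC for EFS | Mean Z, planned | Mean Z, adjusted | Power, planned | Power, adjusted | Equivalent extra events |
|---|---|---|---|---|---|
| 0.65 | 3.389 | 3.426 | 85.8% | 86.9% | 2.2% |
| 0.70 | 3.440 | 3.527 | 87.4% | 88.9% | 5.1% |
| 0.75 | 3.518 | 3.704 | 87.2% | 89.8% | 10.9% |
| 0.794 | 3.601 | 3.927 | 89.9% | 94.4% | 18.9% |

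Rows use 6,000 trials, except 0.75, which uses 3,000. The simulation error on each power is about 0.4 to 0.6 points; another run at 0.70 gave 86.5% and 87.6%. At AUROC 0.60 the gain is 0.9%. On 90.3 events, 5.1% is about 5 events and 18.9% about 17.

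**Step 4: sensitivity.**

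- 40 to 60% of subjects above 9.76: gain of 4.5 to 5.6% at AUROC 0.70 and 16 to 22% at 0.794.
- 80% of events found only at the Week 48 and Week 240 biopsies: 1.9% at 0.65, 4.2% at 0.70, 14.8% at 0.794.
- Risk that truly steps at 9.76: gain 0.04%, that is, nil.
- ELF not prognostic, hazard ratio 0.50: planned 84.3%, adjusted 84.0%, so nothing lost beyond simulation error.
- No treatment effect, nominal 2.5%: rejection rate 2.48% planned and 2.66% adjusted (standard error 0.2 points).

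**The case against.** The planned test has no fault of validity. It matches the randomisation, it is the test on which the sample size was based, and it holds its type I error. A reader might infer that EFS is underpowered, or that the 85% is wrong. The documents do not support either: the 85% reproduces with no ELF adjustment at all.

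A reader might also take 0.794 as ELF's strength for this endpoint and expect a gain of 19%. That does not follow. The figure is for liver-related clinical events in another study, whereas EFS here also counts biopsy-read F4 and all-cause death. The sentence in protocol 1.3 attaches the figure to a score of at least 9.76 and does not say whether it describes the cut or the continuous score. No AUROC for the composite is given, so the lower values are assumptions too.

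Nor is most of the prognostic signal thrown away. On a normal score the split keeps nearly two thirds of it.

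The stricter alpha also shows the gain at its most useful. If both arms pass histology, the Hochberg step can test at 0.05. Converting the powers in the table then gives about 92% against 93% at AUROC 0.70, and 94% against 97% at 0.794.

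Finally, the change has a price: the protocol names the log-rank test, the hazard ratio becomes conditional on ELF, and a functional form must be assumed.

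All of this stands and limits the size of the claim. It does not remove the point, because adjustment gained or was neutral, within simulation error, in every scenario examined.

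**Conclusion.** The point holds as one of efficiency. ELF enters the EFS test and the hazard ratio only in two levels although the score itself is collected, and the documents give no reason for leaving the rest out. The gain from using it is about 1 to 2% more events at an assumed AUROC of 0.60 to 0.65, 5% at 0.70, 11% at 0.75 and, as an upper value, about 19% at 0.794. If most events surface at the two scheduled biopsies, it is 4 to 15% over AUROC 0.70 to 0.794; if risk steps at the cut, it is nil.

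These figures rest on a normal score cut near its median, a log-linear effect and exponential dropout. Exploratory analyses are redacted, so whether an ELF-adjusted model appears there cannot be checked. The change is worth making because it costs little and held the type I error, but its benefit here may be small.

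**What to change.** Before the Week 48 unblinding, amend SAP 6.2.3 as follows.

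- Keep the diabetes and ELF strata and add baseline ELF as a linear continuous covariate to the PHREG model statement. Use the same baseline value that sets the ELF category.
- Take the EFS test and the hazard ratio from this model. Name the test as the score test of treatment. The log-rank code uses a two-arm dataset and the PHREG code a three-arm one, so state which the test uses; the figures above are for two arms.
- Report the stratified log-rank as supportive, and say which test the Kaplan-Meier multiple imputation analysis refers to.
- State that the hazard ratio is conditional on ELF. With event rates of 30% and 16.3%, it would be about 0.44 to 0.48 rather than 0.50.
- Record the departure from protocol 8.6.1 in SAP 6.5 or by protocol amendment.

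The Hochberg and Haybittle-Peto rules in SAP 3.5 can be applied to the new p-values. The cost is one model term and the wording. The downsides are a conditional hazard ratio, an assumed linear form for ELF and a change in the named primary test. If the sponsor prefers to keep the log-rank as primary, the minimum is to prespecify the adjusted model as a sensitivity analysis.

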After the Screening period and a randomization visit at Day 1, study visits will occur on Weeks 1, 4, 8, 12, 16, 20, 24, 28, 32, 36, 40, 44 and 48 and every 12 weeks thereafter until Week 240 with a Follow-Up visit and a Telephone Follow-Up visit. At minimum, review of AEs and concomitant medications and safety laboratory tests will be performed at every visit.

CCI [REDACTED]

While on study, subjects will undergo the following procedures and laboratory assessments:

- Liver biopsy at Week 48 and Week 240 in the Randomized Phase only
- Abdominal ultrasound for HCC surveillance (OL Phase only prior to or on Day 1 and at Weeks 24, 48, 72, 96, 120, 144, 168, 192, 216, and 240)
- Single PK sampling:
  - Randomized Phase at Weeks 1, 4, 12, 24, and 48 in all subjects
  - OL Phase, at all visits in subjects with severe hepatic impairment (Child-Pugh [CP] Class C) in combination with renal impairment ( $eGFR < 30$  mL/min)
- Record subject's stool frequency
- Blood and urine for Biomarkers at Weeks 12, 24, 48, 96, 144, 192, and 240
- HbA1c at Weeks 4, 12, 24, 48, 72, 96, 120, 144, 168, 192, 216, and 240
- Insulin and Lipids at Weeks 4, 12, 24, 48, 72, 96, 120, 144, 168, 192, 216, and 240
- Symptom driven PE, vital signs, body weight, and lifestyle modification counseling
- Waist circumference at Weeks 4, 12, 24, 48, 72, 96, 120, 144, 168, 192, 216, and 240
- HRQoL questionnaires: Short Form 36 [SF-36] Health Survey, Chronic Liver Disease Questionnaire-Nonalcoholic Fatty Liver Disease [CLDQ-NAFLD], Work Productivity and Activity Impairment [WPAI], EuroQol five dimensions [EQ-5D], and Health Resource Utilization questionnaire at Weeks 12, 24, 48, 72, 96, 120, 144, 168, 192, 216, and 240

All subjects will complete the Follow Up visit and a Telephone Follow-Up visit. At the Follow Up visit, subjects will have a symptom driven PE, vital signs, review of concomitant medications and AEs, stool frequency assessment, and safety laboratory tests. A urine pregnancy test will be performed for females of childbearing potential only.

---

**Test Product:** SEL 18 mg oral tablet once daily  
SEL 6 mg oral tablet once daily

---

**Reference Therapy Dose:** PTM SEL 18 mg oral tablet once daily  
PTM SEL 6 mg oral tablet once daily

---

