#### **6.9. Assessments for Premature Discontinuation from Study**

Subjects prematurely discontinuing from the study should complete an ET visit within 30 days of last dose, a Follow-Up visit 4 weeks later, and a Telephone Follow-Up visit 12 weeks after the ET visit.

If a subject is lost to follow-up, survival data may be gathered from public records such as government census or death records (if permitted by local regulations) prior to the completion of the study.

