6.2. Clinical Efficacy Endpoint

6.2.1. Definition of Clinical Efficacy Endpoint

A composite of clinical events that constitute the clinical efficacy endpoint include:

1. Progression to cirrhosis as defined by a liver biopsy showing F4 fibrosis according to the NASH CRN classification as assessed by the central reader
2. Events of hepatic decompensation, including:
 - a) Clinically apparent ascites requiring treatment
 - b) Hepatic encephalopathy (HE) of Grade 2 or above (according to the West Haven criteria defined in Appendix 5 of the protocol) requiring treatment
 - c) Portal hypertension-related upper gastrointestinal bleeding identified by endoscopy and requiring hospitalization, including events of bleeding from esophageal varices, gastric varices, and portal hypertensive gastropathy
3. Liver transplantation or qualification for liver transplantation (defined as MELD score ≥ 15 on at least 2 consecutive occasions at least 4 weeks apart)
4. All-cause mortality

Each of these clinical events (except histologic progression to cirrhosis, all-cause mortality and liver transplantation) will require confirmation by a Hepatic Events Adjudication Committee. The onset date of the first clinical event (biopsy showing F4 fibrosis, death, liver transplantation or adjudication confirmed event) will be used in the analysis.

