7.1.7. Additional Analysis of Adverse Events

7.1.7.1. Cardiovascular Events

Proportion of subjects with adjudication-confirmed cardiovascular events will be summarized by treatment group for the Randomized and OL Phase. Multiple events will be counted only once per subject in each summary for each phase. All adjudicated cardiovascular events will be listed for All Randomized Analysis set.

Time to the first cardiovascular event will be assessed in Randomized Phase. Time (in months) to the first cardiovascular event/censoring date will be calculated as: $(\text{first cardiovascular event date or censoring date} - \text{randomization date} + 1) / 30.4375$. Censoring date will be the latest date among the last visit date in the Randomized Phase, the latest AE onset date in the Randomized Phase, the day prior to OL Study Day 1 for subjects discontinued from the Randomized Phase, and the data cut date for ongoing subjects in the Randomized Phase (for the Week 48 Interim Analysis only).

For the purpose of analysis, if the onset date of a cardiovascular event or an AE is incomplete, the first day of the month (if date is missing) or the first day of the year (if date and month are missing) will be used to derive the first cardiovascular event/censoring date. If such imputation leads to an imputed event date that is earlier than the randomization date, then the randomization date should be used to impute the incomplete event date.

Proportional hazards model will be used to calculate the point estimate and 95% CI for the hazard ratio between SEL 18 mg (SEL 6 mg) and placebo controlling for stratification factors.

For each treatment group, KM estimates of cardiovascular event probability at 3-month intervals (ie, at Month 3, 6, 9, etc) and 95% CIs will be provided. The 95% CIs will be calculated based on Greenwood's formula and log-log transformation of the survival function.

Median, Q1 and Q3 of the time to the first cardiovascular event will be provided for each treatment group. The 95% CI for median EFS based on Brookmeyer-Crowley method {[Brookmeyer 1982](#)} of inverting a generalization of the sign test for censored data will also be provided for each treatment group.

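### SAP 6.2.3 and 7.1.7.1 impute incomplete event dates to the start of the month or year with only randomization as a floor, so an event can be dated before visits at which the subject was documented alive or free of that event

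*SAP*

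**What the plan says.** SAP 6.2.1 takes "The onset date of the first clinical event" into the EFS analysis. For incomplete dates, SAP 6.2.3 substitutes "the first day of the month (if date is missing) or the first day of the year (if date and month are missing"). It adds one correction: "If such imputation leads to an imputed event date that is earlier than the randomization date, then the randomization date should be used".

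SAP 7.1.7.1 applies the same convention to time to first cardiovascular event: "if the onset date of a cardiovascular event or an AE is incomplete, the first day of the month (if date is missing"), and "the first day of the year (if date and month are missing) will be used to derive the first cardiovascular event/censoring date". The floor is again randomization: "then the randomization date should be used to impute the incomplete event date".

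Neither section refers to the last visit, the last date known alive or the last negative assessment as a lower limit for an event date. The EFS sensitivity analyses in SAP 6.2.3 are liver-related death only and the Kaplan-Meier multiple imputation of SAP 3.6.1. The latter imputes times for censored dropouts and leaves partly dated events as they are.

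The protocol collects what a better floor needs. Visits are at Weeks 1 and 4, every 4 weeks to Week 48, "and every 12 weeks thereafter until Week 240" (synopsis, Study Procedures/Frequency). Adverse events are reviewed at each of them. Protocol 6.11.5 has the site assess ascites and hepatic encephalopathy at all visits except the two follow-up contacts, and monitor MELD at each visit.

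**The concern.** A start-of-period rule picks the earliest date consistent with the recorded fragment and ignores everything else known about the subject. Where the subject was seen between that date and the true event, the analysis date contradicts the trial's own records.

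Such a date shortens time to event, puts the event in an earlier risk set and lowers the Kaplan-Meier curve too soon. SAP 6.2.3 reports EFS at 3-month intervals. It can also move an event across the Week 48 data cut if events are counted by analysis date, and SAP 3.5 uses the Week 48 and Week 240 event counts for the Haybittle-Peto adjustment.

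Censoring dates are already protected. SAP 6.2.3 takes the later of last visit and latest AE onset, and SAP 7.1.7.1 takes the latest of several dates, so a back-dated AE cannot pull censoring before an attended visit. Event dates have no such protection.

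**Working it through.** **The plan's own figure.** The only stated figure for EFS is 85% power (SAP 1.3), and this point neither disputes nor depends on it. Expected events in one comparison without dropout are 160 × 0.30 + 320 × 0.163 = 100.2. Schoenfeld's formula with 2:1 allocation, HR 0.50 and two-sided 0.025 gives 84.8%. With 20% exponential dropout (90.2 events), Freedman's formula gives 86.8% and Schoenfeld's 80.6%.

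**Literal records** (dates chosen for illustration, visits on schedule).

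| Randomized | True event | Known as | Analysis date | Days early | Months from randomization, true → imputed | Scheduled visits passed |
|---|---|---|---|---|---|---|
| 3 Jul 2017 | 20 Dec 2019 | 2019 | 1 Jan 2019 | 353 | 29.6 → 18.0 | Weeks 84, 96, 108, 120 |
| 3 Jul 2017 | 28 May 2018 | 2018 | 1 Jan 2018 | 147 | 10.8 → 6.0 | Weeks 28, 32, 36, 40, 44 |
| 3 Jul 2017 | 29 Mar 2018 | Mar 2018 | 1 Mar 2018 | 28 | 8.9 → 8.0 | Week 36 (12 Mar 2018) |

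The floor can itself produce an impossible record. A subject randomized in June 2018 whose death is known only as 2018 is dated on the randomization date, giving (0 + 1)/30.4375 = 0.03 months, however many visits followed.

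**Average size.** Assumptions: event day uniform over Days 1 to 1680 (240 × 7), randomization dates spread over 700 days, all scheduled visits attended. The count is of visits strictly between the imputed and the true date, over 100,000 draws.

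| | Day missing | Day and month missing |
|---|---|---|
| Mean days early | 15 | 169 |
| Maximum days early | 30 | 365 |
| At least one scheduled visit passed | 23% | 89% |
| – event up to Week 48 | 49% | 94% |
| – event after Week 48 | 16% | 88% |
| Most visits passed | 2 | 13 |
| Randomization floor applies | 0.9% | 10% |

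Half a year would be about 182 days; the randomization floor brings the year-only mean down to 169. The maximum of 13 visits arises in the 4-weekly period. At 12-week spacing a full year holds about four visits (365/84 = 4.3). A shift of 169 days is 169/(3 × 30.4375) = 1.85 of the 3-month reporting intervals.

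**Effect on the test.** The simulation had 320 against 160 subjects, true HR 0.50, 70% event-free at Week 240 on placebo, 20% exponential dropout, an unstratified log-rank test and 400 runs per row. The shares of year-only events are assumptions, since the documents give none.

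| Year-only share, SEL / placebo | Power, true → imputed dates | HR, true → imputed dates |
|---|---|---|
| 5% / 5% | 87.25% → 87.25% | 0.462 → 0.462 |
| 10% / 10% | 82.5% → 82.25% | 0.473 → 0.473 |
| 100% / 100% | 83.0% → 82.75% | 0.475 → 0.475 |
| 0% / 20% | 88.0% → 88.75% | 0.460 → 0.457 |

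Each row is a separate set of runs, so only the change within a row is informative. A change of 0.25 points is one run in 400. The HR is the one-step estimate exp[(O − E)/V], which falls below 0.50 under 2:1 allocation.

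**The case against.** The case for leaving the rule alone is that it is a prespecified, reproducible fallback, identical in all arms, for a residual set of records.

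- **Few events are exposed.** F4 progression is dated by biopsy and MELD qualification by laboratory samples. Bleeding events require endoscopy and hospitalization. Decompensation and cardiovascular events are adjudicated, SAEs are transmitted within 24 hours of the investigator's knowledge (Protocol 7.3), and SAP 2.3 holds the final analysis until queries are resolved or judged unresolvable. This stands: year-only dates should be rare.
- **Inference hardly changes.** A reader might infer that the rule biases the EFS comparison. The simulation does not support that: even with 20% year-only dates on placebo alone the HR moves from 0.460 to 0.457. The cardiovascular analysis specifies no hypothesis test.
- **Traced deaths are a weaker example than they look.** Protocol 6.9 lets "survival data may be gathered from public records such as government census or death records" for subjects lost to follow-up, who no longer attend visits. If the death falls in a later year (or later month, for a day-missing date) than the last contact, the imputed date already follows that contact. The conflict needs both in the same period, and the 89% and 23%, which assume full attendance, do not describe these subjects.
- **Not every incomplete date yields a contradiction.** A reader might take each imputed record to be wrong. In about 77% of day-missing cases no scheduled visit is passed, and any imputation, including the one proposed here, can miss the true date.
- **An event-free contact does not always exist for every component.** Ascites and encephalopathy are not assessed at the follow-up contacts, and F4 status is known only at biopsy. A single event-free floor would not work; it must be specific to the component.

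These points limit the importance and shape the fix. None supplies the missing floor.

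**Conclusion.** The point holds as a minor one. Followed literally, SAP 6.2.3 and 7.1.7.1 can date an event before contacts that rule it out, and nothing elsewhere in either document prevents this. This is a stated rule that gives impossible times for some records, so it goes beyond a missing detail.

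The shifts and visit percentages in the working rest on uniform event times and full attendance. The number of affected records is unknown and probably small. The documents do not support reading this as a threat to the EFS test or hazard ratio. What improves is the accuracy of individual event times, of the 3-monthly Kaplan-Meier estimates, and of event counts around the Week 48 cut.

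**What to change.** In SAP 6.2.3 and 7.1.7.1, impute an incomplete event date as the latest of:

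1. the first day of the known month or year;
2. the randomization date;
3. the day after the last documented contact negative for that component: last known-alive date for death; last visit with a negative ascites or encephalopathy assessment for those events; last AE review without the event for bleeding and cardiovascular events.

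The result must not fall after the end of the known month or year, or after the date the event was reported. If a documented onset precedes the visit at which it was reported, the documented onset governs. Biopsy-, MELD- and transplant-dated events keep their procedure or sample dates.

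For subjects attending as scheduled, this cuts the largest year-only back-shift from 365 days to about one visit interval: roughly 4 weeks up to Week 48 and 12 weeks afterwards, plus the visit window. The cost is a short component-specific rule in two SAP sections and its programming, with no new data or procedures. SAP 1 requires any change after finalization to be documented in the clinical study report.
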